## 2.4.3. Phase 3 Exploratory Endpoints

The exploratory endpoints in the Phase 3 portion of the study are:

- Change from Baseline in blood concentrations of CXCL10 after treatment with CMP-001
- Baseline, and change from Baseline, in tumor or blood measurements of biomarkers related to TLR9 (data from Phase 2 portion of the study)

## 3. INVESTIGATIONAL PLAN

# 3.1. Overall Study Design

This is a randomized, open-label, active-control study of first-line CMP-001 administered by intratumoral (IT) injection in combination with intravenous (IV) nivolumab versus nivolumab monotherapy in subjects with Stage III or IV unresectable or metastatic melanoma who have not been previously treated with a programmed cell death protein 1 (PD-1) blocking antibody for metastatic disease. Subjects will be randomized in a 1:1 manner to Arm A to receive CMP-001 IT in combination with nivolumab IV or Arm B to receive nivolumab monotherapy according to the Schedule of Assessments (Table 1) and Section 5.1.

The study will follow a Phase 2/3 design. Eligible subjects will be enrolled in the Phase 2 portion of the study; enrollment into the Phase 3 portion of the study will not proceed until the primary endpoint of Phase 2 is evaluated.

The Phase 2 primary endpoint of ORR per RECIST v1.1 as determined by BICR will be assessed approximately 30 weeks after the last subject is randomized into the Phase 2 portion of the study. If the primary endpoint of Phase 2 is met, subjects enrolled in the Phase 2 portion of the study will continue to receive study treatment (in Arm A or Arm B) in the Phase 3 portion of the study, and enrollment will proceed in Phase 3. If the Phase 2 primary endpoint is not met, subjects enrolled in Phase 2 may remain in the study and continue to receive study treatment until a reason for treatment discontinuation is reached but no further subjects will be enrolled. An Independent Data Monitoring Committee (IDMC) will review safety and efficacy data throughout the study.

Disease assessments by computed tomography (CT) or magnetic resonance imaging (MRI) and other appropriate measures will be performed beginning predose at Week 10 Day 1 (W10D1) (-7 days) and will be repeated every 6 weeks (eg, W16D1). Responses (CR, PR, iCR, or immune PR [iPR]) will be confirmed by a follow-up disease assessment performed at least 4 weeks after the initial response date. Disease assessments will continue every 6 weeks while the subject is on treatment. Disease assessments will be conducted every 12 weeks for subjects on study after 1 year. All scans should be performed at least 2 weeks after the previous CMP-001 IT injection to prevent injection-related pseudoprogression. Imaging should not be delayed for delays in treatment.

[figure not shown]
Subjects may continue to receive study treatment beyond progressive disease (PD) according to RECIST v1.1 and will be evaluated by the Investigator according to iRECIST. Subjects with PD per RECIST v1.1 as determined by Investigator assessment should remain on treatment per Investigator discretion and have a follow-up scan performed at least 4 weeks after the initial date of PD to confirm progression per RECIST v1.1.

Subjects who discontinue study treatment should complete an end of treatment (EOT) visit and 100-day safety follow-up contact, which should occur 100 days (+7) after EOT or until an alternative cancer treatment is initiated, whichever occurs first. Subjects who are post-treatment but have not met criteria for study discontinuation should remain on study for post-treatment follow-up (PTFU) and long-term survival follow-up (LTSFU) and receive study evaluations for efficacy according to the Schedule of Assessments (Table 1).

At the end of the treatment period (2 years), the Sponsor will not continue to provide supplied study treatment to subjects/investigators unless the Sponsor chooses to extend the study. The Investigator should ensure that the subjects receive appropriate standard of care to treat the condition under study.

The study design for is summarized in Figure 1.

Figure 1: CMP-001-011 Study Schema

Abbreviations: 100DFU = 100-Day Follow-up; EOT = End of Treatment; LTSFU = Long-Term Survival Follow-up; IT = intratumoral; IV = intravenous; PTFU = Post-treatment Follow-up; Q3W = every 3 weeks; Q6W = every 6 weeks; Q12W = every 12 weeks; QW = weekly; W1D1 = Week 1 Day 1; W10D1 = Week 10 Day 1.

## 3.2. Duration of Treatment with Nivolumab

The optimal duration of immunotherapy is an important question and continues to be investigated. Clinical trials across different tumors types in the nivolumab and ipilimumab development program indicate that most of the responses occur early, with a median time to response of 2 to 4 months, and emerging data suggest that benefit can be maintained in the absence of continued treatment. A retrospective pooled analysis of 2 melanoma studies suggest the majority of patients who discontinue nivolumab and/or ipilimumab for toxicity maintain disease control in the absence of further treatment (Schadendorf-2017). Furthermore, a limited duration of ipilimumab, including only 4 induction doses, resulted in long-term survival in patients with metastatic melanoma, with a sustained plateau in survival starting around 2 years after the start of treatment (Schadendorf-2015).

Accumulating data suggest that 2 years of treatment with a PD-1 checkpoint inhibitor may be sufficient for long-term benefit. CA209003, a dose-escalation cohort expansion trial evaluating the safety and clinical activity of nivolumab in patients with previously treated advanced solid tumors (including 129 subjects with NSCLC), specified a maximum treatment duration of 2 years. Among 16 subjects with NSCLC who discontinued nivolumab after completing 2 years of treatment, 12 subjects were alive >5 years and remained progression-free without any subsequent therapy. In the CA209003 NSCLC cohort, the OS curve begins to plateau after 2 years, with an OS rate of 25% at 2 years and 18% at 3 years (Brahmer-2017). These survival outcomes are similar to Phase 3 studies in previously treated NSCLC, in which nivolumab treatment was continued until progression or unacceptable toxicity (2-year OS rates of 23% and 29%, and 3-year OS rates of 16% and 18% for squamous and non-squamous NSCLC, respectively) (Felip-2017).

Taken together, these data suggest that treatment beyond 2 years is unlikely to confer additional clinically meaningful benefit and that the risk of progression after discontinuing treatment at 2 years is low.

a The first CMP-001 dose (W1D1) may be administered subcutaneously or by IT injection at the discretion of the Investigator.

In contrast, a shorter duration of nivolumab of only 1 year was associated with increased risk of progression in previously treated patients with NSCLC, suggesting that treatment beyond 1 year is likely needed. In CA209153, patients with previously treated advanced NSCLC who completed 1 year of nivolumab therapy were randomized to either continue or stop treatment, with the option of retreatment upon progression. Among 163 patients still on treatment at 1 year and without progression, those who were randomized to continue nivolumab had significant improvement in (PFS compared to those who were randomized to stop treatment, with median PFS (post-randomization) not reached vs 10.3 months, respectively; hazard ratio (HR) = 0.42 (95% CI: 0.25, 0.71). With a median follow-up of 14.9 months post-randomization, there also was a trend for patients on continued treatment to live longer (OS HR = 0.63 [95% CI: 0.33, 1.20]). Of note, the PFS curves in both groups plateau approximately 1 year after randomization (ie, 2 years after treatment initiation), suggesting that there may be minimal benefit in extending treatment beyond a total of 2 years (Spigel-2017).

Collectively, these data suggest that there is minimal if any benefit derived from continuing immune-oncology treatment beyond 2 years in advanced tumors. Even though immunotherapy is well tolerated, subjects will be at risk for additional toxicity with longer term treatment. Therefore, in this study, treatment will be given for a maximum of 2 years from the start of study treatment.

## 3.3. Blinded Independent Central Review Committee

On-treatment disease assessments (MRI, CT scans, and photographic images) will be assessed by a BICR committee using RECIST v1.1 (see Section 7.2.). Further details are provided in the BICR charter.

# 3.4. Independent Data Monitoring Committee

An external IDMC will review interim safety and efficacy data during the study. The IDMC will make recommendations to the Sponsor throughout the study to ensure subject safety.

Members of the IDMC must not be involved with the study in any other way and must have no competing interest that could affect their roles with respect to the study.

The IDMC will have a finalized charter before their first meeting. Details regarding the roles and responsibilities of IDMC members, meeting facilitation, and proper documentation of IDMC reports will be provided in the charter.

## 4. SELECTION AND WITHDRAWAL OF SUBJECTS

## 4.1. Inclusion Criteria

Subjects enrolled in the study must meet all of the following inclusion criteria to be eligible.

- 1. Histologically or cytologically confirmed unresectable Stage III or Stage IV melanoma per American Joint Committee on Cancer (AJCC) Cancer Staging Manual Eighth Edition.
- 2. Measurable disease, as defined by RECIST v1.1 and all of the following:
  - a. At least 1 accessible lesion amenable to repeated IT injection
  - b. One or more measurable lesions at least 1 cm in diameter that are not intended for CMP-001 injection and can be followed as target lesions per RECIST v1.1
- 3. Able to provide tissue from a core or excisional/incisional biopsy (fine needle aspirate is not sufficient). A newly obtained biopsy (within 90 days before the first dose of study treatment) is mandatory, but an archival sample is acceptable if no intervening therapy for melanoma/cancer was received.

Note: For tissue sampling details, please refer to the Laboratory Manual.

- 4. Adequate organ function based on most recent laboratory values within 3 weeks before the first dose of study treatment on W1D1:
  - a. Bone marrow function:
    - neutrophil count ≥1500/mm^3
    - platelet count ≥100 000/mm³
    - hemoglobin concentration ≥9 g/dL
    - white blood cell >2000/mm^3
  - b. Liver function:
    - total bilirubin  $\leq 1.5 \times$  the upper limit of normal (ULN) with the following exception: subjects with Gilbert Disease total serum bilirubin  $\leq 3 \times$  ULN
    - aspartate aminotransferase (AST) and alanine aminotransferase  $\leq 3 \times ULN$
  - c. Lactate dehydrogenase ≤2 × ULN
  - d. Renal function: estimated (Cockcroft-Gault) or measured creatinine clearance ≥30 mL/min
  - e. Coagulation
    - International normalized ratio (INR) or prothrombin time (PT) ≤1.5 × ULN, unless subject is receiving anticoagulant therapy, as long as PT or partial thromboplastin time (PTT) is within therapeutic range of intended use of anticoagulants
    - Activated partial thromboplastin time or ≤1.5 × ULN, unless subject is receiving anticoagulant therapy, as long as PT or PTT is within therapeutic range of intended use of anticoagulants

- 5. Eastern Cooperative Oncology Group (ECOG) Performance Status of 0 to 1 at Screening.
- 6. Age  $\geq$ 18 years at time of consent.
- 7. Capable of understanding and complying with protocol requirements.
- 8. Women of childbearing potential must have negative serum pregnancy test prior to dosing at W1D1 and be willing to use an adequate method of contraception (Section 4.3.2) from the time of consent until at least 150 days after the last dose of study treatment.
- 9. Able and willing to provide written informed consent and to follow study instructions. Subjects unable to provide written informed consent on their own behalf will not be eligible for the study.

## 4.2. Exclusion Criteria

Subjects presenting with any of the following will not qualify for entry into the study:

- 1. Uveal, acral, or mucosal melanoma.
- 2. Received prior systemic treatment for melanoma in the unresectable or metastatic setting. Prior adjuvant therapy is acceptable if the treatment course (of approximately 1 year duration) was completed and there was no recurrence within 6 months of the last dose of adjuvant treatment.
- 3. Received prior therapy with CMP-001.
- 4. Requires systemic pharmacologic doses of corticosteroids greater than the equivalent of 10 mg/day prednisone within 30 days before the first dose of study treatment on W1D1.
  - a. Subjects who are currently receiving steroids at a prednisone-equivalent dose of  $\leq 10 \text{ mg/day}$  do not need to discontinue steroids prior to enrollment.
  - b. Replacement doses, topical, ophthalmologic, and inhalational steroids are permitted.
- 5. History of CTCAE v5.0 Grade 4 immune-related AE due to adjuvant CTLA-4 or PD-1 blocking antibody.
- 6. Not fully recovered from AEs (to Grade 1 or less [per CTCAE v5.0], with the exception of persistent alopecia, adrenal insufficiency, and hypothyroidism) due to prior treatment.
- 7. Active pneumonitis, history of pneumonitis that required steroids, or history of interstitial lung disease.
- 8. Severe uncontrolled cardiac disease within 6 months of Screening, including but not limited to poorly controlled hypertension, unstable angina, myocardial infarction, congestive heart failure (New York Heart Association Class II or greater), pericarditis within the previous 6 months, cerebrovascular accident, and implanted or continuous use of a pacemaker or defibrillator.
- 9. Known history of immunodeficiency.
- 10. Known additional malignancy that has progressed or required active treatment within the past 3 years. Exceptions include basal cell carcinoma of the skin, squamous cell

carcinoma of the skin that has undergone potentially curative therapy, curatively treated localized prostate cancer with prostate-specific antigen level below 4.0 ng/mL, in situ cervical cancer on biopsy or a squamous intraepithelial lesion on Papanicolaou smear, thyroid cancer (except anaplastic), and adjuvant hormonal therapy for breast cancer > 3 years from curative-intent surgical resection.

- 11. Active autoimmune disease that has required systemic treatment in past 2 years; replacement therapy is not considered a form of systemic treatment.
- 12. Untreated, symptomatic, or enlarging central nervous system (CNS) metastases or carcinomatous meningitis (including leptomeningeal metastases from solid tumors).
- 13. Prior allogenic tissue/solid organ transplant.
- 14. Known or suspected active infection with severe acute respiratory syndrome coronavirus 2 virus (SARS-CoV-2).
- 15. Active infection requiring systemic therapy.
- 16. Known or suspected infection with HIV, hepatitis B virus, or hepatitis C virus; testing is not required unless suspected.
- 17. Received a live/attenuated virus vaccination within 30 days prior to the first dose of study treatment on W1D1.
- 18. Received blood products (including platelets or red blood cells) or colony stimulating factors (including granulocyte colony stimulating factor, granulocyte/macrophage colony stimulating factor, or recombinant erythropoietin) within 30 days prior to the start of Screening.
- 19. History of permanent discontinuation of nivolumab due to infusion reactions.
- 20. Any concurrent uncontrolled illness, including mental illness or substance abuse, which in the opinion of the Investigator, would make the subject unable to cooperate or participate in the trial.
- 21. Participation in another clinical study of an investigational anticancer therapy or device within 30 days before the first dose of study treatment on W1D1.
  - Note: Participation in the follow-up phase (receiving no study treatment) of a prior study is allowed.
- 22. Requires prohibited treatment (ie, non-protocol specified anticancer pharmacotherapy, surgery, or conventional radiotherapy) for treatment of malignant tumor.
- 23. Has a life expectancy of less than 3 months and/or has rapidly progressing disease (eg, tumor bleeding, uncontrolled tumor pain) in the opinion of the treating Investigator.
- 24. Pregnant or breast-feeding or expecting to conceive or donate eggs within the projected duration of the study, from the time of consent until at least 150 days after the last dose of study treatment for women.

# 4.3. Women of Childbearing Potential

A woman of childbearing potential is considered fertile following menarche and until becoming postmenopausal unless permanently sterile (Section 4.3.1). If fertility is unclear and a menstrual cycle cannot be confirmed before the first dose of study treatment (W1D1),

subject should be considered of childbearing potential and applicable pregnancy tests completed.

## 4.3.1. Women of Non-Childbearing Potential

Female subjects must meet 1 of the following criteria to be considered of non-childbearing potential:

- Have undergone hysterectomy or bilateral salpingectomy/oophorectomy or bilateral tubal occlusion/ligation at least 1 month before Informed Consent.
- Are medically confirmed to be post-menopausal. A postmenopausal state is defined as 12 months of amenorrhea before W1D1 in a woman over age 45 years in the absence of other biological or physiological causes.
   In addition, females under the age of 55 years must have a serum follicle stimulating hormone, (FSH) level > 40 mIU/mL on 2 measurements done 2 months apart to confirm menopause.

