#### 7.1.13. Pregnancy Testing

Pregnancy testing will be performed on women of childbearing potential at the time points specified in the Schedule of Assessments (Table 1). A central serum pregnancy test is required during Screening. Women of childbearing potential must have a negative serum or urine pregnancy test (minimum sensitivity 25 IU/L or equivalent units of human chorionic gonadotropin) prior to dosing at W1D1 as specified in Table 1. Urine pregnancy testing will be completed for time points after Screening. If a urine pregnancy test is positive at any time point, the test must be confirmed with a serum sample. If a serum pregnancy test is required based on a positive urine pregnancy test, serum test results must be confirmed as negative prior to enrollment or subsequent treatment of the subject.

If the serum test confirms the subject is pregnant, they must have the EOT visit and the pregnancy must be reported.

Hepatitis B and C

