# APPENDIX J. WOMEN OF CHILDBEARING POTENTIAL DEFINITION AND METHODS OF CONTRACEPTION

#### DEFINITIONS

#### Woman of Childbearing Potential (WOCBP)

A woman is considered fertile following menarche and until becoming post-menopausal unless permanently sterile. Permanent sterilization methods include hysterectomy, bilateral salpingectomy, and bilateral oophorectomy.

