#### Women in the following categories are not considered WOCBP

- Premenarchal
- · Premenopausal female with 1 of the following:
  - Documented hysterectomy
  - Documented bilateral salpingectomy
  - Documented bilateral oophorectomy

Note: Documentation can come from the site personnel's review of the participant's medical records, medical examination, or medical history interview.

- Postmenopausal female
  - A postmenopausal state is defined as 12 months of amenorrhea in a woman over age 45 years in the absence of other biological or physiological causes. In addition, females under the age of 55 years must have a serum follicle stimulating hormone, (FSH) level > 40 mIU/mL to confirm menopause.

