## CONTRACEPTION GUIDANCE FOR FEMALE PARTICIPANTS OF CHILD BEARING POTENTIAL

One of the highly effective methods of contraception listed below is required during study duration and until the end of relevant systemic exposure, defined as 5 months after the end of study treatment.\*

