#### Highly Effective Methods That Are User Independent

- Implantable progestogen-only hormonal contraception associated with inhibition of ovulation b
- Intrauterine hormone-releasing system (IUS)c
- Intrauterine device (IUD)c
- Bilateral tubal occlusion
- Vasectomized partner

A vasectomized partner is a highly effective contraception method provided that the partner is the sole male sexual partner of the WOCBP and the absence of sperm has been confirmed. If not, an additional highly effective method of contraception should be used.

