#### Sexual abstinence

Sexual abstinence is considered a highly effective method only if defined as refraining from heterosexual intercourse during the entire period of risk associated with the study drug. The reliability of sexual abstinence needs to be evaluated in relation to the duration of the study and the preferred and usual lifestyle of the participant.

- It is not necessary to use any other method of contraception when complete abstinence is elected.
- WOCBP participants who choose complete abstinence must continue to have pregnancy tests, as specified in Section 2.
- Acceptable alternate methods of highly effective contraception must be discussed in the event that the WOCBP participants chooses to forego complete abstinence

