#### COLLECTION OF PREGNANCY INFORMATION

Guidance for collection of Pregnancy Information and outcome of pregnancy is provided in Section 7.1.13 and Section 8.3.2.

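### Section 4.3.1 and Appendix J of the protocol disagree on whether a premenopausal woman with tubal occlusion is of childbearing potential, and so on whether she has scheduled pregnancy tests (minor inconsistency)

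*Protocol*

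**What the plan says.** **Section 4.3.1** lists ways to be classed as non-childbearing, any one of which is enough. One is "bilateral tubal occlusion/ligation at least 1 month before Informed Consent". No menopausal condition is attached. Section 4.3 refers to 4.3.1 for what permanently sterile means.

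**Appendix J** defines the same status differently. "Permanent sterilization methods include hysterectomy, bilateral salpingectomy, and bilateral oophorectomy". Its list of women who are not of childbearing potential has the entry "Premenopausal female with 1 of the following", followed by those three procedures only. Its contraception guidance for women of childbearing potential opens with "One of the highly effective methods of contraception listed below is required during study duration", and the user-independent methods under it name "Bilateral tubal occlusion".

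**Testing** depends on this status. Section 7.1.13 states: "Pregnancy testing will be performed on women of childbearing potential". The Table 1 note and inclusion criterion 8 carry the same restriction.

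**Cross-references in Appendix J** are uneven. Women who choose abstinence "must continue to have pregnancy tests, as specified in Section 2", but Section 2 holds the objectives and endpoints. The closing line on pregnancy information "is provided in Section 7.1.13 and Section 8.3.2", which are the right sections.

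**FSH wording** also differs. For women under 55, Section 4.3.1 asks for two raised values 2 months apart, the Table 1 note schedules one test at Screening, and Appendix J gives no count.

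**The concern.** The two texts give opposite answers for one identifiable group, and nothing in the protocol says which governs. Appendices D and E say how to resolve a discrepancy with their source publications; Appendix J has no such rule. The SAP's precedence statement covers only the analysis of data.

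What is at stake is safety monitoring. Pregnancy is an exclusion (criterion 24) and a reason to stop treatment (Section 4.5). A site that follows 4.3.1 would dose such a woman with no scheduled test, so an early pregnancy would come to light only through symptoms, self-report or an unscheduled test.

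**Working it through.** The check is mainly a comparison of texts. The case is a premenopausal woman whose tubal occlusion was done at least 1 month before consent.

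| Question | Section 4.3.1 | Appendix J |
|---|---|---|
| Is tubal occlusion a route to non-childbearing status? | Yes, sufficient alone | No, not on the list |
| Is it contraception for a woman of childbearing potential? | Not applicable | Yes |
| Resulting status | Non-childbearing | Childbearing potential |
| Scheduled pregnancy tests | None | Screening, W1, W4, W7, every 3 weeks, EOT |
| Contraception duty | None | Met by the occlusion |

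**Can the texts be reconciled?** The word include in Appendix J's sterilization sentence might leave room for other methods. It does not help, because the list of women not of childbearing potential is enumerated and tubal occlusion is placed on the contraception side. The Section 4.3 default for unclear fertility does not help either. It applies when fertility is unclear and a menstrual cycle cannot be confirmed, whereas 4.3.1 settles this woman's status.

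**Which text would a site follow?** Section 4.3 and the Table 1 note both cite 4.3.1. I found no reference to Appendix J in the body of the protocol. The likely practice is therefore no scheduled tests.

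**Number of scheduled tests under Appendix J.** Tests = Screening + visits every 3 weeks from W1 + EOT. If the last visit is week w, the number of visits is (w − 1)/3 + 1.

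- One dose: 1 visit + 2 = 3
- 26 weeks (assumed): W1 to W25, (25 − 1)/3 + 1 = 9 visits, + 2 = 11
- 52 weeks (assumed): W1 to W52, (52 − 1)/3 + 1 = 18 visits, + 2 = 20
- 104 weeks (protocol maximum): W1 to W103, (103 − 1)/3 + 1 = 35 visits, + 2 = 37

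Under 4.3.1 the count is 0 in every row. The 37 assumes no dosing delays, so it is an upper figure.

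**How long the conflict can apply.** SAP II.C gives the last enrollment as 01Jun2022, and SAP II.F allows treatment up to the 2-year limit: 01Jun2022 + 2 years is about June 2024.

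**FSH.** Under 4.3.1 a woman under 55 needs two values. A site relying on the single Screening test in the Table 1 note, or on Appendix J, could class her as postmenopausal, and so untested, on one value. The Screening window in Table 1 is 30 days, so two values 2 months apart cannot both fall inside it.

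**The case against.** The strongest reply is that sites have one operative answer. The body cites 4.3.1, and Section 4.3.2 does not name tubal occlusion as contraception, which fits 4.3.1. On this view the fault is an appendix that was never reconciled with the body. That is fair as to what sites probably did. It does not remove the contradiction, and the text that prevails in practice is the one that tests less.

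Safeguards also remain. Exclusion 24 bars pregnant women whatever their classification, Sections 7.1.12 and 7.4 allow extra tests when clinically indicated, and Section 8.3.2 requires a pregnancy to be reported within 24 hours of awareness. All of this stands, but each depends on someone suspecting or knowing of the pregnancy.

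Aligning Appendix J to 4.3.1 would also end the conflict. That is a legitimate option, but it would drop tests that one of the protocol's own texts requires. Appendix J lists tubal occlusion beside intrauterine devices and a vasectomized partner, whose users are tested. Sharing a list does not prove equivalence, so the preference for testing is a judgement, supported by its low cost.

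Some stronger readings are tempting and are not supported:

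- **A contraception gap.** There is none: 4.3.1 requires no contraception of her, and under Appendix J the occlusion meets the requirement.
- **Tubal occlusion is unacceptable because 4.3.2 omits it.** That list is open: it sets a failure-rate criterion and then gives methods it includes.
- **The FSH mismatch is harmless because it leads to more testing.** That holds only where the two-value rule is followed.
- **The SAP needs a line on definitions.** SAP VII.A has one descriptive row on childbearing potential, but a SAP sentence cannot recover which definition a site applied.

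**Conclusion.** The inconsistency is real and minor. It is an error in the text and not a design choice. For a premenopausal woman with tubal occlusion at least 1 month before consent, scheduled pregnancy tests number 0 under Section 4.3.1 and 3 to 37 under Appendix J, depending on time on treatment. A reader might take 37 missed tests as a measure of harm; it counts procedures only.

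The number of affected women is not given. It may be zero and cannot exceed the number of women among the 20 randomized. Women with hysterectomy, bilateral salpingectomy or bilateral oophorectomy are not touched by the tubal-occlusion conflict, nor are postmenopausal women; the separate FSH point concerns women under 55. A reader might look for an effect on the trial's results, but no endpoint, power or error rate depends on this.

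The conclusion rests on reading Appendix J's list of women not of childbearing potential as complete. That she is of childbearing potential follows from that list together with the placement of tubal occlusion under contraception; Appendix J does not say it in one sentence.

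**What to change.** 1. Remove tubal occlusion/ligation from the non-childbearing list in Section 4.3.1, so that these women are tested as in Appendix J.
2. For clarity, name it among the methods in Section 4.3.2. The list is open, so this is helpful but not strictly required.
3. Have Section 4.3, the Table 1 note and Appendix J cite one definition.
4. In Appendix J, change the testing reference from Section 2 to Section 7.1.13.
5. Make the two-value FSH rule govern in Section 4.3.1, the Table 1 note and Appendix J, and say where the first value may come from, given the 30-day Screening window.
6. Apply the definition to any such woman still on treatment.

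The cost is protocol wording and a few extra pregnancy tests for women with tubal occlusion. No SAP change is needed.
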